4.0 Background and Significance

Unintended pregnancy continues to be a major public health issue in the United States. In 2002, nearly half of the 6.4 million pregnancies in the United States were unintended.

Almost half of unintended pregnancies end in elective abortion. [9] Further, 80% of adolescent pregnancies are unintended.[10] The need for a highly effective, safe, estrogen-free, compliance independent and rapidly reversible contraception can be readily met with ESI. The etonogestrel subdermal implant has been available worldwide since 1998 and received United States Food and Drug Administration approval in 2006. Though studies have confirmed its efficacy, convenience, and cost-effectiveness, bleeding irregularities account for up to 43% of requests for early removal. [4, 11] though **the rate of 28.5% was reported in our population.** [29] Other reasons for removal include weight gain, headaches, mood changes and desire for pregnancy, each accounting for about 10-15% of removal requests.[11] Published data regarding bleeding management in US women is limited. A multicenter trial of 330 US women reported a 13 % removal rate for “bleeding pattern changes,” particularly within the first 8 months of use, consistent with international studies. [1, 2]. However, prior trials have excluded women weighing over 130% of ideal body weight [4]. Our retrospective study was the first US study to include women regardless of BMI.[3] Further, an expanded retrospective cohort of 337 women confirmed the efficacy of Doxycycline as 44% of women who received Doxycycline requested removal and 92% of those who received another intervention or declined intervention beyond reassurance requested removal [29]. A recent review of the literature includes interventions for bleeding but admits limited or anecdotal support for these. Further, the first line intervention contains estrogen, which is contraindicated in many ESI users [26]. The intervention in this proposed study is hormone-free.

Rationale for using Doxycycline as initial treatment for ESI related bleeding Doxycycline 100 mg twice daily for 10 days

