5.3 Measurements of Study Variables

5.3.1 Study Process

a. Enrollment

Subjects who meet the eligibility criteria will be required to sign an informed consent form and HIPAA authorization prior to enrollment. Subjects will receive identification numbers at this time and will be considered enrolled into the study. Patient demographic characteristics, prior contraceptive method, postpartum and breastfeeding status will be recorded. All subjects will undergo a history and physical examination including pelvic examination, height and weight if this was not done within an age-appropriate interval. A baseline BMI will be calculated. A Pap test using ThinPrep[®] will be obtained if none has been taken in the preceding 12 months. A retrospective symptom diary to date of ESI insertion and prospective symptom diaries for the duration of the study will be provided to the patient with instructions to contact study personnel if materials are lost or more are needed.

b. Randomization

Patients enrolled in the study at the time of ESI insertion who either report unacceptable bleeding when contacted by study personnel at 13 weeks post-ESI insertion or self-report unacceptable bleeding after 13 weeks post ESI insertion will be offered randomization to placebo or Doxycycline. Randomization will be done with stratification based on: age (< 30 years, ≥ 30 years), postpartum status and body mass index (BMI < 30, BMI ≥ 30). The randomization will be performed using a dynamic allocation approach based on the Pocock-Simon method to ensure a balance in the treatment groups across the stratification levels. The randomization assignment for each patient will be obtained upon entering the patient's stratification levels into a web-based application created and supported by the Division of Biomedical Statistics and Informatics. Investigators and patients will be blinded to group assignment. For this reason, all pills will be made to look identical. **Enrollment of new patients will continue until approximately 100 patients are randomized (50 in each group).** Additional patients will need to be enrolled given the lower than expected reported unacceptable bleeding rates.

c. Placebo group

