interval to allow for assessment of efficacy of each course of Doxycycline. Rates of unacceptable bleeding in all patients remaining in the study at 26 weeks post-randomization will be calculated and participation in the study will end. If patients request ESI removal at any time during the study after randomly assigned treatment, study participation will be recorded as a **removal**. Method satisfaction will be assessed at removal and study participation will end. Patients will be provided with alternative contraception of choice at their expense. **Need for additional treatment at >4 weeks post-randomized treatment will represent the primary endpoint.** Satisfaction with ESI at randomization, and 13 and 26 weeks post randomization, and method continuation at 26 weeks post-randomization represent the secondary endpoints.

j. Post-treatment Followup

All patients will be contacted by study personnel at 26 weeks (\pm 2 weeks) post-randomization for final satisfaction survey and weight. Study completion BMI will be calculated. All diaries will be collected for analysis and patients will receive remuneration. When all patients complete the study, the data will be unblinded for analysis.

k. Special Considerations

If patients receive randomized treatment toward the end of the 39 week study interval (rather than at about 13 weeks post ESI insertion), post-treatment data for at least 13 weeks will be collected for a maximum study length of 52 weeks post-ESI insertion.

l. Additional testing

Additional laboratory testing or imaging for heavy or unusual bleeding will be individualized as clinically indicated.

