5.3.2 Outcome measurements

A. Primary treatment efficacy and safety end point (primary endpoint addressing specific aim #1)

- The efficacy of Doxycycline on ESI-related bleeding will be compared to placebo based on rates of **unacceptable bleeding** and weekly prospective symptom diary at 13 weeks post-randomization.

B. Primary treatment efficacy and safety endpoints (secondary endpoints addressing specific aim #1)

- Method continuation rate at 13 weeks post-randomization will be compared for women in the Doxycycline vs. placebo group.
- Bleeding patterns will be quantified based on the PBLAC and WHO classification of clinically important bleeding patterns over each 13 week reference period.[13,14, 29].
- Incidence of additional symptoms including acne, headache, mood changes in the treatment groups will be compared to placebo at randomization and 13 weeks post-randomization based on the weekly prospective symptom diary
- Interval to recurrence of unacceptable bleeding post-randomized treatment (i.e., need for additional treatment) will be determined
- Rate of adverse events associated with medical treatment will be documented by prospective symptom diary and BMI calculation. These include headache, mood changes, acne and change in BMI.

C. Patient satisfaction with primary treatment endpoint (primary endpoint addressing specific aim #2)

- Patient satisfaction with ESI at randomization for a baseline pre-treatment satisfaction and at 13 weeks post-randomized treatment following primary treatment with Doxycycline vs. placebo will be compared

D. Patient satisfaction with secondary treatment endpoint (primary endpoint addressing specific aim #2)

- Patient satisfaction with ESI at 26 weeks post-randomized treatment for patients with continued unacceptable bleeding following primary treatment who receive secondary treatment with Doxycycline will be calculated.

E. Secondary treatment efficacy and safety endpoint (primary endpoint addressing specific aim #3)

- Method continuation rate at 26 weeks post-randomized treatment for patients with continued unacceptable bleeding after primary treatment who undergo secondary treatment with Doxycycline will be calculated

F. Secondary treatment efficacy and safety endpoint (secondary endpoints addressing specific aim #3)

- Rate of ESI removal for bleeding between 13 and 26 weeks post randomization.

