10.1.1 Remuneration

Patients will receive \$25 after each interval of 13 weeks for completion of prospective symptom diary (and pill diary if applicable) and satisfaction survey. Patients who discontinue study participation prior to completion of each 13 week set of diaries/satisfaction survey, those who do not turn in all diaries/satisfaction survey or turn in incomplete diaries/satisfaction survey will not receive this remuneration. Patients who complete the study will receive \$50.00 upon receipt of final set of diaries, satisfaction survey and study coordinator clinic visit.

[name] Investigator

- Proposal and associated material preparation
- IRB approval process
- patient consent, patient satisfaction surveys, bleeding diary preparation
- study marketing within Mayo and to MHS sites
- training and oversight of study personnel, troubleshooting
- clinical appointments for concerns
- progress report preparation
- data analysis
- manuscript preparation/submission/revision

[name]

- study marketing within Mayo and to MHS sites
- training and oversight of study personnel, troubleshooting
- clinical appointments for concerns

Study coordinator

- Patient Consent & Enrollment
- (available on-call for routine GYN clinic, scheduled for women responding to advertising)
- Available for phone contact by subjects throughout the study (triage of subject concerns)
- Phone contacts at 13 weeks for all subjects (450+)
- Clinic visits for “unacceptable bleeding” and randomization (150+)
- Phone contact at 26 weeks for all subjects
- Clinic visit at 39 weeks for all subjects

- Potential additional post-39 week phone contact for limited # subjects with late randomization
- Baseline - Consent form copying & scanning
- Baseline – data collection / case report form completion
- Subject education re: diary completion, study plan, subject responsibilities
- Collection of subject diaries at 13 – 26 – 39 weeks
- Assessing treatment compliance for randomized and secondary treatment
- Satisfaction surveys at 13 – 26 – 39 weeks
- Documentation of study participation, randomization, and follow-up in medical record
- Data entry into electronic database (clinical data, diary data, satisfaction survey data)
- Maintain subject binders / folders (150+ complex and 300+ simple)
- Organize and develop system for follow-up visits and phone calls
- Scheduling of follow-up visits (prefer to have support of the PAC office)
- Remuneration for all subjects
- Consent form development

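### Change in BMI is listed as an adverse event of study treatment, but it is measured from implant insertion, has no listed weight at removal, and has no analysis method that fits it

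*Combined protocol and SAP*

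**What the plan says.** - **Outcome.** Section 5.3.2 B: "Rate of adverse events associated with medical treatment will be documented by prospective symptom diary and BMI calculation". The list that follows reads: "These include headache, mood changes, acne and change in BMI". No size of change is given that would count as an event.
- **First BMI.** Section 5.3.1.a, at enrollment, which takes place at implant insertion: "height and weight if this was not done within an age-appropriate interval. A baseline BMI will be calculated". If a recent enough weight is on file, the baseline may therefore predate insertion.
- **Randomization.** Section 5.3.1.b places it at the 13-week contact or later. BMI enters as a stratification class (below 30, or 30 and above). No new weight is stated.
- **Last BMI.** Section 5.3.1.j, at 26 weeks (plus or minus 2) "post-randomization for final satisfaction survey and weight. Study completion BMI will be calculated".
- **Removal.** Section 5.3.1.i: "Method satisfaction will be assessed at removal and study participation will end". No weight is listed.
- **Late randomization.** Sections 5.3.1.k and 7.1 promise at least 13 weeks of follow-up and cap the study at 52 weeks from insertion.
- **Analysis.** Section 5.4.2 gives chi-square and logistic models for categorical endpoints (including presence of adverse events), Kaplan-Meier and Cox methods for binary versions of them, and Poisson models for diary days.

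**The concern.** If BMI change is to describe study treatment, it should start when study treatment starts. Here it starts at insertion, so weeks of implant use before any study drug are mixed in. Women whose implant is removed appear to leave without a closing weight. That loss may be related to the outcome, because Section 4.0 says: "Other reasons for removal include weight gain, headaches, mood changes and desire for pregnancy, each accounting for about 10-15% of removal requests". It may also differ by arm, since Section 8.4 expects fewer removals for bleeding on doxycycline.

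The planned methods also cannot take a BMI change as it stands. Someone would have to choose a cut-off or a model later, possibly after seeing the data. At stake is whether one named safety outcome can be reported in an interpretable way.

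**Working it through.** **The plan's own figure.** The documents give no figure for BMI change. The Aim 1 power reproduces: with 44% vs 80%, 50 per arm and a pooled chi-square test, power = Φ[(0.36 − 1.96·√(2·0.62·0.38/50)) / √((0.44·0.56 + 0.80·0.20)/50)] = Φ(1.88) = 97%, in line with the stated figure of above 90%. It does not bear on this point.

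**1. Share of the interval before study drug** = weeks to randomization / (weeks to randomization + follow-up weeks).
- Randomized at week 13, weighed 26 weeks later: 13/39 = 33% (32% to 35% across the ±2-week window: 13/41 to 13/37).
- Randomized at week 26, weighed 26 weeks later: 26/52 = 50%.
- Randomized at week 39 with 13 weeks of follow-up: 39/52 = 75%. This is the extreme case; Section 10.1.1 expects only a limited number of late randomizations.

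A woman randomized after week 26 reaches her 26-week contact after the 52-week cap, and no other closing weight is defined for her.

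**2. Loss of precision.** Let T be weeks from insertion to the closing weight, and F weeks from randomization to it. The ratio is the SD of change from insertion over the SD of change from randomization. The documents give no SD or course for weight, so three assumptions are shown.

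| Assumption | Ratio | T=39, F=26 | T=52, F=13 |
|---|---|---|---|
| Weight varies around a stable level | 1 | 1.0 | 1.0 |
| Variance grows in proportion to time | √(T/F) | 1.22 | 2.0 |
| Steady individual trends | T/F | 1.5 | 4.0 |

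For illustration, take a true difference of 0.6 SD (SD of change since randomization; an assumed effect) and 50 per arm. Power = Φ(0.6·√25/ratio − 1.96), which is 85% at ratio 1.0, 69% at 1.22 and 52% at 1.5.

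**3. Missing closing weights.** Section 3.3 sets a continuation benchmark above 75%, for women having secondary treatment only. At 75%, 0.25 × 66 = 16.5 of the 66 such women expected in Section 5.4.1 would have none. Assuming 75% to 95% continuation in all 100 randomized women, 25 to 5 would have none. With 10% to 15% of removals due to weight gain, 25 removals give 2.5 to 3.75 such women over both arms, and 5 removals give fewer than one.

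**4. Method.** Set against Section 5.4.2, a BMI change is not a category without a cut-off, not a time to event, and not a count of diary days. None of the listed methods applies to it as written.

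**5. What a 26-week comparison measures.** Section 5.4.1 expects 44% of the doxycycline arm and about 80% of the placebo arm to request additional treatment: 50 × 0.44 + 50 × 0.80 = 62 women by these rates (the plan states 66). That treatment is open-label doxycycline. A comparison at 26 weeks is therefore one of initial assignment, not of drug against no drug.

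**The case against.** - **The insertion baseline does not bias the comparison.** A reader might infer that it does. Randomization balances earlier weight change in expectation, so the cost is precision. This stands.
- **Removals for weight gain are not lost.** A reader might infer that they drop out. Section 2 (under aim 3) records the reason and date for removal before 26 weeks from enrollment, and Section 5.3.2 F enumerates reasons between 13 and 26 weeks after randomization. For a woman randomized at week 13 the two windows cover her whole follow-up; a later randomization may leave a gap. What is missing is the closing weight. This stands.
- **Insertion is the natural baseline for an implant effect.** Section 4.0 ties weight gain to the implant, and the doxycycline reactions in Section 6.2.3 do not include it. That is fair, but Section 5.3.2 B assigns BMI change to medical treatment and Section 5.4.2 compares adverse events by arm, so the mismatch remains.
- **Removed women might still be weighed.** Section 5.3.1.j speaks of all patients, and Section 5.2 calls the records easy to abstract. Section 5.3.1.i, however, ends participation at removal. The text is unclear, so a missing closing weight is probable, not certain.
- **Chance events.** One might argue that about half of women would show an event by chance if any rise counted. The plan contains no such rule, so the argument has no footing.

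**Conclusion.** The point holds as a minor one. At least about 33% of the BMI interval precedes study drug, and more for women randomized late. The effect on the arm comparison is noise, with an SD ratio between 1.0 and 1.5 in the usual case depending on an assumption that the documents cannot decide. Change within an arm cannot be attributed to study treatment. Closing BMI is probably missing after removal: 5 to 25 of 100 women if continuation is 75% to 95%, of whom fewer than one to about four would have left for weight gain. No listed method fits the measure.

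The documents do not support reading this as a biased safety comparison or as a failure to record removals for weight gain. The primary endpoint and sample size are untouched.

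**What to change.** 1. Record weight at the randomization clinic visit, already budgeted in Section 10.1.1, and at removal, or abstract it from the record. State which closing weight applies to women with less than 26 weeks of follow-up after randomization.
2. Take change in BMI out of the yes/no adverse-event list.
3. Compare closing BMI (26 weeks, removal, or the defined late weight) between arms in a linear model adjusted for BMI at randomization, age group and postpartum status, with a 95% CI.
4. Do not adjust for weeks since randomization in the main model: removal partly sets that time, and removal is itself a post-randomization outcome. Show 26-week completers as a sensitivity analysis.
5. Label the result a comparison of initial assignment, because many women in both arms are expected to receive open-label doxycycline before 26 weeks.
6. Report insertion-to-end change separately, pooled over arms, as a description of the implant period.

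Cost: a weight at visits that already take place and a short paragraph in Section 5.4.2. The downside is that closing weights fall at differing times, which for removals may be anywhere up to 26 weeks. A weight neither taken nor charted at the time cannot be recovered later.

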2.0 Specific Aims

2.1 Specific Aim #1 (primary aim):

- To determine the effect of Doxycycline vs. placebo on the need for additional treatment for unacceptable bleeding at 13 weeks post-randomized treatment.

2.2 Specific Aim #2 (secondary aim):

- To determine if initial treatment with Doxycycline results in higher patient satisfaction with ESI as compared to placebo at 13 weeks post-randomized treatment.

2.3 Specific Aim #3 (secondary aim):

- To determine method continuation and patient satisfaction rate at 26 week post-randomization in patients who choose secondary treatment with Doxycycline for unacceptable bleeding at 13 weeks post-randomized treatment.

In order to evaluate specific aim #1:

- All ESI patients will be offered enrollment in the study at ESI insertion and will begin prospective diaries. They will be contacted at 13 weeks post insertion. If patients report unacceptable bleeding at that time or self-report at any time following an initial 13 week interval, they will be offered randomization to Doxycycline or placebo. Patients will continue a weekly prospective symptom diary for the duration of study.
- Time to recurrence of unacceptable bleeding post-treatment and need for secondary treatment (primary endpoint) will be determined by completion of prospective symptom recording by 13 weeks post-randomized treatment.

- Side-effects and adverse events associated with medical treatment will be documented.

In order to evaluate specific aim #2:

- A patient satisfaction survey will be administered at randomization and 13 weeks post-randomization. The results will be compared between the Doxycycline and placebo study arms.

In order to evaluate specific aim #3:

- Patient satisfaction will be assessed at 13 weeks post-ESI insertion.
- Patients who report unacceptable bleeding after initial randomized treatment and who choose additional treatment will receive secondary treatment with Doxycycline and the method continuation rate and patient satisfaction rate at 26 weeks post randomization will be calculated.
- In patients who leave the study prior to 26 weeks post-randomization, patient satisfaction will be recorded at that time.
- If ESI is removed prior to 26 weeks post-enrollment, the reason, date of removal and alternative contraception will be documented.

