3.0 Study Hypotheses

3.1 Study hypotheses for specific aim #1 (primary aim):

- Doxycycline is more effective than placebo in the initial management of ESI-related bleeding.
- **Statistically significant difference between the placebo and Doxycycline groups will be shown in favor of Doxycycline**

3.2 Study hypotheses for specific Aim #2 (secondary aim):

- Patients in the Doxycycline group will report a higher satisfaction rate with ESI scores on a survey as compared to those in the placebo arm at 13 weeks post-randomization.
- **Statistically significant difference in patient satisfaction rates between the placebo and Doxycycline groups will be shown in favor of Doxycycline.**

3.3 Study hypotheses for specific aim #3 (secondary aim):

- In patients who request secondary treatment for unacceptable bleeding, administration of Doxycycline will result in a high method continuation rate and patient satisfaction rate at 39 weeks post ESI insertion.
- The above will be supported by method continuation rate of >75% [3, 8] at 26 weeks post-randomization.

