5.2.1 Patient selection

After appropriate IRB approval, ESI users aged 18-51 years old who meet the inclusion and exclusion criteria, and sign a written consent will be **enrolled in the study at the time of ESI insertion**. Every effort will be made to insert ESI on the same day as consent unless medically contraindicated. They will complete a prospective symptom diary from date of ESI insertion. All patients will be contacted by study personnel 13 weeks after enrollment and queried as to the presence of unacceptable bleeding. Bleeding concerns will be objectively assessed using a modification of the Pictorial Blood Loss Assessment Chart (PBLAC) [27]. Patient-initiated contact in with bleeding concerns at any time after 13 weeks post ESI insertion will result in enrollment and randomization at the time of contact. **The basis for randomized treatment will be whether or not the bleeding is “unacceptable” to the patient. This is inherently subjective, but constitutes the basis for most removal requests.** Patients who report unacceptable bleeding at 13 weeks post-ESI insertion, and those who call with bleeding concerns after 13 weeks post ESI insertion, will be randomized into two groups (Doxycycline or placebo). Patients who do not report unacceptable bleeding will continue to complete diaries and may be eligible for randomized treatment if unacceptable bleeding develops. Patients will receive diaries sufficient for completion of the study with instructions to contact study personnel if more diaries are needed or if diaries are lost. Patients and investigators will be blinded to the group assignment as well as the study coordinator who will be responsible dispensing of appropriate study medication by the pharmacy.

Patients who continue to have unacceptable bleeding after 4 weeks post-randomized treatment and wish to have secondary treatment will be treated with Doxycycline. Secondary treatment will not be blinded. Rates of unacceptable bleeding and patient satisfaction scores at 26 weeks post-randomized treatment in remaining study participants will be calculated.

[figure not shown]

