- Normal bleeding frequency (3-5 bleeding episodes).
- Frequent bleeding (more than 5 bleeding episodes),
- Prolonged bleeding (1 or more bleeding episodes lasting 14 days or more)

Subgroup analysis may provide additional insight into the efficacy of treatment for various bleeding patterns.

g. Patient satisfaction surveys

Patients will be asked to fill out short satisfaction surveys at randomization measuring satisfaction prior to any treatment, and at 13 and 26 weeks post randomization (see appendix). If patient has their ESI removed prior to 26 weeks post randomization, she will be given a final satisfaction survey at removal. Patient satisfaction surveys will be recorded on a paper formate or via Mayo Clinic website RED Cap.

Patients will rate their satisfaction with a) ESI and b) bleeding with ESI on a 5-point Likert scale ranging from very satisfied to very dissatisfied. If patient has ESI removed prior to 26 weeks post-study enrollment, she will be given a final satisfaction survey at removal.

h. Treatment issues

At enrollment, patients will be provided with a contact number allowing them to reach study personnel at all times with concerns. Instructions will be provided for instances of drug intolerance/allergy, heavy bleeding or other ESI related issues and clinical appointments for evaluation scheduled as needed.

i. Secondary Treatment

If a patient reports unacceptable bleeding at >4 weeks post randomization to treatment or placebo, study participation will be recorded as **need for additional treatment, and will represent the primary endpoint**. If she wishes to have secondary treatment, she will be treated with Doxycycline. Treatment will be limited to two interventions per 13 week

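### Aim 3 reads continuation at 26 weeks from randomization although the secondary course can start at very different times, so the rate has no fixed follow-up and depends on start times

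*Combined protocol and SAP*

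**What the plan says.** **Endpoint and criterion.** Section 5.3.2.E gives the main endpoint for Aim 3 as "Method continuation rate at 26 weeks post-randomized treatment for patients with continued unacceptable bleeding after primary treatment who undergo secondary treatment with Doxycycline". Section 3.3 adds: "The above will be supported by method continuation rate of >75% [3, 8] at 26 weeks post-randomization". The same section also refers to 39 weeks after insertion, which is the same date only for a woman randomized at week 13.

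**When secondary treatment may start.** Section 5.2.1: "Patients who continue to have unacceptable bleeding after 4 weeks post-randomized treatment and wish to have secondary treatment will be treated with Doxycycline". Section 5.3.1.i applies the same rule: "If a patient reports unacceptable bleeding at >4 weeks post randomization to treatment or placebo". Neither gives a latest start. The one further limit, "Treatment will be limited to two interventions per 13 week" interval, caps the number of courses and not how late one may begin. Section 2.3 words the Aim 3 group differently: "patients who choose secondary treatment with Doxycycline for unacceptable bleeding at 13 weeks post-randomized treatment". Section 5.4.1 (under the label Aim 4) places the continued bleeding of the same 66 women at 26 weeks after insertion, which is week 13 for a woman randomized at week 13.

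**Removals.** Section 5.3.2.F lists "Rate of ESI removal for bleeding between 13 and 26 weeks post randomization" and a matching rate for other reasons.

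**End of follow-up.** Participation ends at 26 weeks after randomization (Section 5.3.1.i). Women randomized late may be followed for as little as 13 weeks, up to 52 weeks from insertion (Sections 5.3.1.k and 7.1).

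**Analysis.** Section 5.4.2 plans a 95% CI around the continuation estimate. Its time-to-event fallback is for poor compliance with follow-up and is not timed from the secondary course.

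**The concern.** Section 5.4.1 says the purpose is to estimate continuation following additional treatment. The endpoint's clock starts at randomization instead, so a woman's time at risk after the second course is 26 minus the week in which she started it. One proportion then mixes women observed for very different lengths of time. Late starts raise it, because little time remains in which a removal can occur. Early starts lower it. Two trials with the same outcome after the second course could report different rates, and fall on different sides of 75%, only because women asked for treatment at different times.

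Two gaps go with this. Women followed for only 13 weeks after randomization may have no week-26 value, and no rule says how they enter the denominator. In addition, the 5.3.2.F window opens at week 13, so a removal between an early second course and week 13 is missing from those rates.

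**Working it through.** **1. The plan's own figure.** Section 5.4.1 gives a 95% half-width of ±10% around 75% with n = 66. Check: 1.96 × √(0.75 × 0.25 / 66) = 0.104. It reproduces. (The plan's own rates give 50 × 0.44 + 50 × 0.80 = 62 women rather than 66; the half-width is then 10.8%.) This precision treats all women as sharing one follow-up time.

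**2. Follow-up after the start of the second course.**
- Earliest start, week 4: 26 − 4 = 22 weeks.
- Section 2.3 reading, starts by week 13: from 26 − 13 = 13 weeks to 22 weeks.
- Sections 5.2.1 and 5.3.1.i, no latest start: from 22 weeks towards 0.
- Randomized at week 39 and ended at week 52: 52 − 39 = 13 weeks in all, so at most 13 − 4 = 9 weeks after a second course.

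**3. Illustration of the effect.** The documents give no start times and no removal hazard, so both are assumed here. Let S22 be true continuation 22 weeks after the second course and take a constant hazard λ = −ln(S22)/22. Expected continuation at week 26 for a start at week w is exp(−λ(26 − w)). For follow-up even over a to b weeks, the mean is [exp(−λa) − exp(−λb)] / [λ(b − a)].

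With S22 = 65%, λ = 0.4308/22 = 0.01958:
- Start at week 4: 65%; week 13: 78%; week 18: 86%; week 24: 96%.
- Starts even over weeks 4-13 (follow-up 13-22 weeks): (0.775 − 0.650)/(0.01958 × 9) = 71%.
- Starts even over weeks 4-24 (follow-up 2-22 weeks): (0.962 − 0.650)/(0.01958 × 20) = 80%.

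Expected week-26 rate for other values of S22:

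| S22 | All at week 4 | Even, weeks 4-13 | All at week 13 | Even, weeks 4-26 |
|---|---|---|---|---|
| 50% | 50% | 58% | 66% | 72% |
| 56% | 56% | 63% | 71% | 76% |
| 60% | 60% | 67% | 74% | 78% |
| 66% | 66% | 72% | 78% | 82% |

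The S22 at which the expected rate equals 75% is 75%, 70%, 61% and 55% for the four start patterns, in column order.

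**4. Removals outside the 5.3.2.F window.** With S22 = 65% and starts even over weeks 4-13, time from start to week 13 is even over 0-9 weeks. Mean continuation at week 13 is (1 − exp(−0.1762))/0.1762 = 91.7%. About 8 of the 29 removals per 100 women (100 − 71) therefore fall before week 13 and are not in F.

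**5. Would 75% carry over to a 13-week horizon?** Under the same model, 13-week continuation exceeds 75% whenever S22 exceeds 0.75^(22/13) = 61.5%. The 65% case passes, since S13 = 77.5%.

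**The case against.** **The week-13 reading.** Section 2.3, the removal window in 5.3.2.F and the Aim 4 statement in 5.4.1 can all be read as secondary treatment settled by week 13. Follow-up is then about 13 to 22 weeks, and with starts even over weeks 4-13 the illustration (71%, or 67% at S22 = 60%) stays below 75%. This stands as a limit on size. It does not settle the matter: the operative Sections 5.2.1 and 5.3.1.i say otherwise, follow-up still varies by 9 weeks, and late-randomized women are still shorter.

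**A stronger reading is tempting.** A reader might infer that late starters will carry the rate over 75% and that the Aim 3 hypothesis will be wrongly declared supported. The documents do not support that. It needs many starts well after week 13 and an assumed hazard, and early starts push the other way.

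**Removals in F.** A reader might also infer that F's window hides early failures from the 75% criterion. It does not. A woman treated at week 5 whose implant is removed at week 10 counts as a non-continuer in E and in the 13-week continuation rate of 5.3.2.B. Only the F rates are incomplete.

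**Consequence.** Aim 3 is secondary, uncontrolled and unblinded, and is planned as an estimate with an interval. Continuation at a fixed study week is also a legitimate summary of the whole strategy. Both points stand, and they are reasons to keep the week-26 rate as a description. Finally, any endpoint that begins at the second course is conditional on reaching it, so that feature is no argument against the present definition.

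**Conclusion.** The concern holds in a limited form. The Aim 3 continuation rate is anchored to randomization while the treatment it describes can start at widely different times, so it has no fixed meaning as continuation after secondary doxycycline. The range of follow-up is arithmetic from the protocol: 13 to 22 weeks on one reading, 22 weeks to almost none on the other, and at most about 9 weeks for the latest-randomized women.

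The effect on the rate is not known. In the 65% illustration it is the difference between 71% and 80%, and that rests on an assumed constant hazard and assumed start times. The distortion can go either way. The randomized comparison in Aim 1 is not touched.

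**What to change.** - **Reconcile the text.** Bring Sections 2.3, 3.3, 5.3.2.F and 5.4.1 into agreement with 5.2.1 and 5.3.1.i on when secondary treatment occurs. Which rule applies is for the sponsor to decide.
- **Re-anchor the estimate.** Estimate Aim 3 continuation by Kaplan-Meier from the start of the first secondary course, censoring at the end of planned follow-up, at a prespecified horizon with a 95% CI. This also gives women with short follow-up a defined place in the analysis.
- **State the horizon for 75%.** Say to which horizon the criterion applies and why. It should not be moved to 13 weeks without justification, because under a constant hazard that is a looser bar than 75% at 22 weeks.
- **Removals.** Count the 5.3.2.F removals, for bleeding and for other reasons, in secondary-treated women from the same start date.
- **Data.** Record the start date of secondary treatment and all removal dates to the end of follow-up. Section 2.0 asks for the removal date only up to 26 weeks after enrollment, and no section expressly requires the start date, although the pill counts for each course make it obtainable.
- **Describe.** Report the distribution of start times, and keep the week-26 rate as a descriptive result.

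The cost is protocol wording, two date fields and analysis. The interval will be somewhat wider, because late starters contribute little to a fixed horizon.
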